8.4 Confirmatory Measures/Duration of Response (see Table 10 for specific PCWG3 measures)

8.4.1 Confirming time-to-event outcomes

Any post-treatment change in disease status, be it favorable or unfavorable, should be confirmed using a second assessment at a later time 6-8 weeks.

8.4.2 Duration of overall response

Duration of overall response is measured from the time when partial response or complete response is first noted until the date when recurrent or progressive disease is objectively documented. Duration of overall complete response is measured from the time the criteria for complete response are first met until the first date that recurrent disease is objectively documented. Duration of stable disease is measured from the start of treatment until the criteria for progression are met.

8.4.3 Progression-free survival

Progression-free survival (PFS) is a composite endpoint defined as the time from study entry or random assignment to disease progression in bone or soft-tissue, symptoms, or death. Use an interval-censored approach in which all assessments of the composite PFS endpoint (i.e., PSA, bone, CT scans, and symptom assessments) are performed at the same time points. All assessments of disease should be collected at the same time interval (e.g., bone scan, CT scan, and PSA at 12-week intervals). In addition to PSA, confirm post-treatment changes in measurable target lesions, radionuclide bone scans, and symptoms.

Table 10. Prostate Cancer Clinical Trials Working Group 3 (PCWG3) Outcome Measures.

Variable	Control/Relieve/Eliminate Endpoints	Prevent/Delay Endpoints
PSA	Record the percent change from baseline (rise or fall) at 8 weeks and, separately, the maximal change (rise or fall) at any time using a waterfall plot	Decline from baseline: record time from start of therapy to first PSA increase that is ~25% and ~2.0 ng/mL above the nadir, and which is confirmed by a second value 3 or more weeks later (i.e., a confirmed rising trend) † Recording the duration of PSA decline of little value No decline from baseline: PSA progression ~25% and ~2.0 ng/mL after 8 weeks
Soft-tissue lesions	Use RECIST with caveats: Only report changes in lymph nodes that were ~2 cm in diameter at baseline Record changes in nodal and visceral soft tissue sites separately Record complete elimination of disease at any site separately Confirm favorable change with second scan Record changes using waterfall plot	Use RECIST criteria for progression, with additional requirement that progression at first assessment be confirmed by a second scan 6 or more weeks later Note that for some treatments, a lesion may increase in size before it decreases
Bone	Record outcome as either new lesions or no new lesions First scheduled reassessment: No new lesions: continue therapy New lesions: perform a confirmatory scan 6 or more weeks later Confirmatory scan: No new lesions: continue therapy Additional new lesions: progression Subsequent scheduled reassessments: No new lesions: continue New lesions: progression	The appearance of ~2 new lesions, and, for the first reassessment only, a confirmatory scan performed 6 or more weeks later that shows at least 2 or more additional new lesions The date of progression is the date of the first scan that shows the change
Symptoms	Consider independently of other outcome measures Document pain and analgesia at entry with a lead-in period and measure repeatedly at 3- to 4-week intervals Perform serial assessments of global changes in HRQOL, urinary or bowel compromise, pain management, additional anticancer therapy Ignore early changes (~12 weeks) in pain or HRQOL in absence of compelling evidence of disease progression Confirm response or progression of pain or HRQOL endpoints ~3 weeks later	

Abbreviations: PSA, prostate-specific antigen; HRQOL, health-related quality of life.

†Particularly important when anticipated effect on PSA is delayed or for biologic therapies.

9. CORRELATIVES

The correlative assessments in this section are proposed as tertiary or exploratory objectives of the study. If exceptional responders/non-responders are observed, the comprehensive sequencing based profiling of tumors is expected to delineate putative molecular biomarkers, and refine the understanding of ESK981's mechanism of action.

9.1 The Association of Somatic and Germline Mutations with Exceptional Response/Resistance to ESK981

In addition to the prevalent TP53 mutations, AR amplifications, and ETS-fusions, mutations in the PTEN-PI3K-AKT pathway as well as germline and somatic events in the DNA repair pathway are frequently observed in mCRPC tumors. We propose integrative genomic sequencing to comprehensively profile the spectrum of genetic aberrations. The specific endpoints will be: activation through a hotspot mutation or amplification (gain-of-function), and inactivation through two-hit missense/nonsense mutation or deletion (loss-of-function) for genes from select pathways recurrently altered in mCRPC. Somatic and germline mutations will be identified through DNA sequencing of tumor and matched patient normal tissue utilizing the Oncoseq1700 platform. NGS-based analyses of copy-number alterations (CNA) and loss-of-heterozygosity (LOH) will be employed to probe for focal amplifications (e.g. AR, CCND1, PIK3CB) and deletions (e.g. PTEN, RB1).

9.2 The Association of ETS / Kinase Gene Fusions with Exceptional Response/Resistance to ESK981

Capture RNA sequencing will be used to detect further genetic events, such as activating and inactivating genes fusions. It is expected that this will identify activating ETS fusions (ERG, ETV1, ET4, ETV5), driver kinase fusions (BRAF, RAF1, FGFR2, FGFR3), as well as additional inactivating events in tumor suppressors (e.g. PTEN, TP53, RB1, BRCA1/2, ATM). To increase statistical power, mutations will be evaluated for association with clinical outcomes, both independently and grouped by molecular pathways: PTEN-PI3K-AKT, homologous recombination (e.g. BRCA1, BRCA2, PALB2), cell-cycle checkpoints (e.g. RB1, CCND1).

9.3 The association of AR signaling with Exceptional Response to ESK981

Furthermore, since modulation of androgen receptor (AR) signaling through tyrosine kinases is observed as a mechanism of resistance to androgen deprivation therapy and androgen-independence, we hypothesize that the loss of dependence on AR signaling will be an additional independent predictor of response and outcomes. The trial is designed to enrich for AR-independent patients in the Enza/Abi-refractory cohort who will allow us to evaluate our hypotheses. Aggregate scores of AR-dependence and AR-independence will be derived from the expression levels of canonical AR targets and trans-differentiation markers.

9.4 Metastatic Kinome Activity Profiles as Predictive Biomarkers for Response to ESK981

Since the mechanism of ESK981 is based on the multiplex inhibition of a set of protein kinases we hypothesize that a tumor's dependence on kinase signaling pathways (kinome activity profile) will correlate with sensitivity to multiplex kinase inhibition by ESK981. Similarly, kinome activity profiles will be quantified through the expression levels of individual tyrosine and serine/threonine kinases targeted by ESK981 and, by proxy of gene expression signatures, the activity of their downstream signaling pathways. The activity of each targeted kinase will be correlated with the clinical endpoints independently, and in conjunction with the tumor's AR status and other genetic alterations.

9.5 Evaluation of Circulating and Disseminated Tumor Cells as Pharmacodynamic Biomarkers of ESK981 response.

The burden of circulating (CTC) and disseminated tumor cells (DTC) has been associated with survival in a number of solid tumors. Further, a decrease in the number of CTC is a reliable indicator of response for a number of oncological therapies. Therefore, we hypothesize that ESK981 treatment will reduce the burden of CTCs in the blood and DTCs obtained from the bone marrow. Blood samples will be collected at intervals of 4 weeks for the total duration of treatment (from screening to end of treatment). Circulating Tumor Cells (CTC) will be enriched from 7.5ml of whole blood using the AdnaTest ProstateCancerSelect assay. The expression of marker genes associated with androgen signaling, cell proliferation, kinome activity, autophagy, will be assessed pre-amplified cDNA (AdnaTest ProstateCancerDetect) using qPCR. In addition, blood samples will be processed using RareCtyle platform for further characterizing CTCs in single cell level. Similarly, to detect DTCs bone marrow aspirates will be collected. DTCs will be enriched by negative (lymphocyte markers) and positive (epithelial markers) selection using flow cytometry. The enriched DTCs will be profiled for single-cell gene expression using the 10X genomics sequencing platform (The Chromium System). Specifically, we will evaluate whether clinical response is associated with: (i) the pre-treatment CTCs/DTC burden, (ii) a reduction in CTCs/DTCs during response, (iii) changes CTC/DTC expression profiles. Forty (40) ml of whole blood will be collected at each respective time-point, please see lab manual for collection and processing guidelines.

9.6 Pathological assessment of phenotypic tumor and host responses to ESK981 treatment.

ESK981 treatment results in a striking and conserved phenotype (autophagy) in preclinical *in vitro* and *in vivo* models. However, the drug can in principle target other kinases expressed in normal cells from the tumor microenvironment for example. To differentiate between the direct and indirect effects of ESK981, we will collect tumor biopsies from baseline and 8 weeks of treatment for histopathological evaluation. We will perform immunohistochemistry (IHC) for the following protein markers: Ki67 (cell proliferation); AR (androgen receptor); CD31, NG2 and desmin (angiogenesis); PDGFR1/2, VEGFR1/2, Tie2, c-Kit, FGFR (tyrosine kinase receptor); LC3 (autophagy). We will evaluate whether treatment response is associated with a phenotypic change in the tumor histology (vacuolization), microenvironment (vascularization, immune infiltration), and the tumor's molecular characteristics (AR status, kinome profile).

10. DATA REPORTING AND REGULATORY REQUIREMENTS

10.1 Data Collection and Management

Data collected during this study will be entered into a secure database.

10.1.1 Electronic Case Report Forms (eCRFs)

Data will be collected and maintained on study specific electronic case report forms in the Oncore Research Enterprise system at Karmanos Cancer Institute. Training and support will be provided for all staff entering data upon local regulatory approval. Data entry must occur within 2 weeks of visits along with submission of applicable source documentation. KCI is responsible for ensuring eCRF's are completed accurately and submitted in a timely manner.

10.1.2 Source documents

Source documentation refers to original records of observations, clinical findings and evaluations that are subsequently recorded as data. Source documentation will be made available to support the subject's research record.

10.1.3 Record retention

The investigator will maintain adequate and accurate records to enable the conduct of the study to be fully documented and the study data to be subsequently verified. After study closure, the investigator will maintain all source documents and study-related documents. Records are to be retained and securely stored until the later of: (a) two (2) years following the date a New Drug Application is approved for the Study Drug that is the subject of the Clinical Trial; or (b) two (2) years after the Investigational New Drug Application for such Study Drug is terminated or withdrawn, or such longer period of time as may be required by Participant policies, applicable laws, rules or regulations.

10.1.4 Data Submission Timelines

All data should be transmitted within 14 days of visit except for SAE submission (see section 7.4).

10.1.5 Data Review and Queries

Karmanos will review data and source documentation as it is submitted. Data will be monitored against source documentation as necessary and discrepancies will be sent as queries. In addition, the Karmanos monitor will review data for logic, consistency, and obvious anomalies. Queries will be sent by the Karmanos monitor.

10.1.6 Protocol Amendments or Changes in Study Conduct

Any change or addition (excluding administrative) to this protocol requires a written protocol amendment that must be reviewed and approved. Amendments significantly affecting the safety of subjects, the scope of the investigation or the scientific quality of the study require additional approval by the IRB. A copy of the written approval of the IRB must be provided. Examples of amendments requiring such approval are:

1. increases in drug dose or duration of exposure of subjects,
2. significant changes in the study design (e.g. addition or deletion of a control group),
3. increases in the number of invasive procedures,
4. addition or deletions of a test procedure required for monitoring of safety.

These requirements for approval should in no way prevent any immediate action from being taken by the investigator or by in the interests of preserving the safety of all patients included in the trial. If an immediate change to the protocol is felt to be necessary by the investigator and is implemented for safety reasons PI must be notified and the IRB at the center must be informed immediately. Amendments affecting only administrative aspects of the study do not require formal protocol amendments or IRB approval but the IRB must be kept informed of such administrative changes. Examples of administrative changes not requiring formal protocol amendments and IRB approval include:

1. changes in the staff used to monitor trials
2. minor changes in the packaging or labeling of study drug

10.2 Data Safety and Monitoring Board

- 10.2.1 Scheduled meetings will be held monthly or more frequently depending on the activity of the protocol. These meetings will include the protocol investigators and data managers involved with the conduct of the protocol.
- 10.2.2 During these meetings the investigators will discuss matters related to:
 - Safety of protocol participants (Adverse Event reporting)
 - Validity and integrity of the data
 - Enrollment rate relative to expectation of target accrual, characteristics of participants
 - Retention of participants, adherence to the protocol (potential or real protocol violations)
 - Data completeness on case report forms and complete source documentation
- 10.2.3 Completed Data and Safety Monitoring Reports of these regular investigator meetings will be kept on file in the office of the Clinical Trials Core (see form in Appendix F). The data manager assigned to the clinical trial will be responsible for completing the report form. The completed reports will be reviewed and signed off by the Principal Investigator (PI) or by one of the Co-PI's in the absence of the PI. The signed off forms will then be forwarded to the Director, Clinical Trials Core for review of completeness and processing with the Data and Safety Monitoring Committee.
- 10.2.4 The Barbara Ann Karmanos Cancer Institute, Data and Safety Monitoring Committee will meet on a monthly basis to review the prior months Serious Adverse Event forms and Data and Safety Monitoring study specific reports that have been filed.

11. STATISTICAL CONSIDERATIONS

11.1 Objectives

The **primary objectives** of this study are:

- 1) To determine the PSA $\geq 50\%$ response rate (PSA50) from baseline using the PCWG3 criteria to ESK981 as a single agent in men with mCRPC who have progressed on enzalutamide (an oral androgen-receptor inhibitor) and/or abiraterone acetate (an androgen synthesis inhibitor).
- 2) To assess the safety and tolerability of ESK981 as a single agent.

The **secondary objectives** of this study are:

- 1) To determine the time to PSA response (TTPR) to ESK981 in patients with mCRPC
- 2) To determine the duration of PSA response (PRD) to ESK981 in patients with mCRPC
- 3) To determine PSA progression rates as defined by the PCWG3 criteria.
- 4) To determine PSA progression free survival (PPFS) as defined by the PCWG3 criteria.

The **correlative/exploratory/tertiary objectives** of this study are: to assess exploratory biomarkers from blood and tumor biopsies. Examples of these may include, but are not limited to: whole exome sequencing, capture whole transcriptome analysis, AR and ARv7 analysis, ki-67, apoptosis, etc.

11.2 Endpoints

11.2.1 The first primary endpoint (PSA50) is a PSA decline of $\geq 50\%$ from baseline (PSA50), using the PCWG3 criteria. Refer to Section 8.2.1.

The second primary endpoint(s) (toxicities) is (are) defined in Section 7. Adverse events of all grades will be captured by the National Cancer Institute - Common Terminology Criteria for Adverse Events, version 4.03 (NCI-CTCAE v4.03) and GCP standards.

11.2.2 The secondary endpoints are defined as follows:

Time to PSA response (TTPR) is defined as the time from treatment start until the first documented occurrence of PSA50. PSA50 is defined in Section 1.3.

Duration of PSA response (PRD) is defined as the time from start of PSA50 until PSA progression (defined in Section 8.3.2).

PSA progression free survival (PPFS) is defined in Section 8.3.2 except that it will be based on PSA assessments only. PSA progression rates will be estimated from the PSA-only PFS distribution.

11.2.3 The correlative/exploratory/tertiary endpoints (and the methods of their determination) are described in Section 9.

11.3 Design

11.3.1 We will utilize a single group single-stage Phase II design for the study. Patients will receive 160mg (4 capsules) of ESK981 dosed once daily for five consecutive days followed by a two consecutive day treatment break, for a cycle of 28 days. After 8 weeks (2 cycles) of ESK981, patients will be evaluated for their rate of PSA decline of $\geq 50\%$ from baseline (PSA50), using the PCWG3 criteria. Extrapolating from the data summarized on PSA50 response at any time by Cheng et al,¹⁶ we hypothesize that the 8-week PSA50 rate in patients similar to patients eligible for this protocol is approximately 20%. We also hypothesize that the 8-week PSA50 rate for ESK981 treated patients will be approximately 30%.

11.3.2 We seek preliminary evidence that the true 8-week PSA50 rate for patients on ESK981 exceeds the hypothesized reference value of 20%. Having a directional hypothesis, the PSA50 rate will be estimated with a 1-sided Wilson type 90% lower confidence interval (CI). With precision defined as a CI half-width (distance from the PSA50 estimate to the lower 90% confidence limit (CL)) of 0.100, a sample size of N=27 patients and a sample estimate of PSA50 = 30% would have a lower CL = 0.201. This would indicate that the true 8-week PSA50 rate was $> 20\%$, with 90% confidence.

11.3.3 The required sample size of N=27 was determined from the "Confidence Intervals for One Proportion" program within the PASS 15 software.¹⁷

11.3.4 Sample size adjustment for non-compliance will be made as follows. A major goal of this study is to evaluate the efficacy (in addition to the effectiveness) of ESK981 upon the PSA50 rate, safety, and tolerability. For each individual patient, we will allow for an ESK981 treatment non-compliance of up to 25% (i.e., up to 25% of pills were not taken).

Our initial analytic focus will be on the patients who are eligible (per Section 3), and evaluable (i.e., were on treatment for at least Cycle 1 [28 days]), and compliant (took at least 75% of the intended ESK981 pills during Cycle 1).

The patients meeting all 3 such requirements will be considered the eligible, evaluable, and compliant ("EEC") subset. We anticipate that up to 15% of the enrolled patients will not become EEC for one reason or another.

To obtain the requisite 27 ESK981 compliant patients (i.e., completely EEC) allowing for an overall attrition rate ("a") of up to 15% of patients, we will need to enroll up to $N' = [N / (1 - a)] = [27 / (1 - 0.15)] = 27 / 0.85 = 32$ patients.

The consequence of non-compliance (i.e. not being completely EEC) is that such patients would still be utilized in analyses of the effectiveness of ESK981. For example, that would focus on the patients who were "EE" but not compliant. Another effectiveness analysis would focus on the patients who were eligible, but neither evaluable or compliant. All of these analyses of non-EEC patients would be viewed as *sensitivity analyses* of the efficacy analysis of only the EEC patients. These supplemental analyses would provide a more complete assessment of the feasibility and efficacy *combined* of the oral ESK981 treatment in this study population.

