3. PATIENT SELECTION

A total of 27 patients with mCRPC will be included in this study.

Each subject will be counseled by a study investigator about the planned study procedures, risk and benefits of participating in the study, and alternative therapeutic options. Each subject must sign an Institutional Review Board (IRB)/ Independent Ethics Committee (IEC)-approved consent form and written authorization to use protected health information as outlined in the Health Insurance Portability Act (HIPAA) of 1996, prior to the initiation of any study related procedures.

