11.4 Analysis

11.4.1 For the Primary Objectives, all analyses point and (1-sided Wilson type 90% lower) CI estimates of the primary endpoint (PSA50) will be calculated.

Adverse events will be tabulated by incidence and severity graded according to the National Cancer Institute – Common Terminology Criteria for Adverse Events (CTCAE) version 4.03. Other statistics will include point and (2-sided) CI estimates of overall toxicity and of specific types of toxicity.

11.4.2 For Secondary Objective 1, descriptive statistics of TTPR will be used to summarize the time to PSA response. These descriptives will include N, median, mean, standard deviation (SD), interquartile range (IQR), minimum, and maximum.

11.4.3 For Secondary Objectives 2 and 3, the censored distributions of duration of response (RD) and PSA progression free survival (PFS) will be summarized with the Kaplan-Meier (K-M) survivorship estimate. A graph of the K-M curve for PRD and for PPFS will be generated along with the Hall-Wellner 90% confidence band, and a display of the number of patients at risk at several time points, below the X-axis. Summary statistics (6-month rate, 12-month rate, median, etc.) will be calculated from the K-M life table, each one with its respective 80% confidence interval (CI).

11.4.4 For the Correlative (Exploratory) Objectives, frequency distributions of all categorical variables (grade of specific types of toxicity, and categorical biomarkers or other correlatives) will be generated. Serial PSA levels will be displayed using spaghetti plots, and changes in PSA using waterfall plots.

Descriptive statistics will be used to summarize all continuous correlatives (e.g., PSA, continuous biomarkers and other correlatives), and changes in them pre/post ESK981 treatment. Gene expression levels will be \log_2 transformed prior to descriptive analysis. Multiple boxplots and scatterplots will be used to display summary statistics of biomarkers/correlatives and interrelationships between continuous correlatives, respectively.

Details of the planned determination of bioinformatics correlatives are given in Section 9. Response (whether PSA50 or overall), a categorical clinical outcome, will be statistically modeled as a function of each correlative using exact logistic regression. TTPR, a continuous

uncensored clinical outcome (limited to only the PSA50 responders), will be statistically modeled as a function of each correlative using linear regression.

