11.5 Expected Accrual Rate, Accrual Duration, and Total Study Duration

- 11.5.1 This will be a clinical trial involving Karmanos Cancer Institute (KCI) only. We expect to accrue 10-12 patients/year.
- 11.5.2 At that rate, we can accrue 32 patients (to obtain 27 EEC patients) in 32-38 months. Allowing an additional 4 months to finish determining all biomarkers and correlatives in all patients yields an estimated total study duration of 36-42 months.

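### The 30% / 0.201 illustration that justifies N=27 cannot be observed: 8/27 does not exclude 20%, and 9/27 is the first count that does

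*Combined protocol and SAP*

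**What the plan says.** Section 11.3.1 takes 20% as the 8-week PSA50 rate in comparable patients and adds: "We also hypothesize that the 8-week PSA50 rate for ESK981 treated patients will be approximately 30" percent. Section 11.3.2 seeks preliminary evidence that the true rate "exceeds the hypothesized reference value of 20" percent. It specifies the method: "the PSA50 rate will be estimated with a 1-sided Wilson type 90% lower confidence interval (CI"). It sets the precision target, measured from the estimate down to the lower limit, at 0.100. The worked result is that "a sample size of N=27 patients and a sample estimate of PSA50 = 30% would have a lower CL = 0.201", and the next sentence concludes that the true rate would then be above 20% with 90% confidence. Section 11.3.3 attributes N=27 to a confidence-interval program for one proportion. Section 11 gives no responder count, power or error rate.

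Section 11.4.1 carries the same interval into the analysis: "all analyses point and (1-sided Wilson type 90% lower) CI estimates of the primary endpoint (PSA50) will be calculated".

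The 27 are patients who are eligible, evaluable and compliant (EEC). Section 11.3.4 inflates for attrition of up to 15%: "To obtain the requisite 27 ESK981 compliant patients (i.e., completely EEC) allowing for an overall attrition rate", it arrives at 32 to enrol. Section 11.5.2 agrees: "we can accrue 32 patients (to obtain 27 EEC patients) in 32-38 months". Section 3 says instead: "A total of 27 patients with mCRPC will be included in this study".

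**The concern.** The illustration clears the 20% reference by only 0.001, and it does so at a fractional number of patients. A reader would reasonably take it to mean that seeing about 30% in 27 patients is enough to conclude that the rate is above 20%. The only attainable result that would be reported as 30% is 8/27, so the question is whether the conclusion holds there.

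Together with the software calculation behind it, this sentence is the plan's only quantitative case for N=27. If it fails at 8/27, the plan understates the result needed and conceals how likely the study is to fall short when the drug performs exactly as hypothesised.

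The analysed number may also differ from 27, since up to 32 may be enrolled, and Section 11.3.2 gives no attainable result for any other denominator. The total in Section 3 adds to the uncertainty about which number is meant.

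**Working it through.** **Inputs.** From Sections 11.3.1 and 11.3.2: n = 27, planning estimate 0.30, reference 0.20, 1-sided 90% Wilson limit (z = 1.28155, z² = 1.64237), target half-width 0.100. From Section 11.3.4: attrition 15%.

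**Formula.** With p = x/n,

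L = [p + z²/(2n) − z·√(p(1−p)/n + z²/(4n²))] / (1 + z²/n)

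At n = 27: z²/(2n) = 0.03041, z²/(4n²) = 0.000563, 1 + z²/n = 1.06083.

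**Step 1: the plan's own figure.** At p = 0.30 the root term is √(0.007778 + 0.000563) = 0.09133, and L = (0.30 + 0.03041 − 1.28155 × 0.09133)/1.06083 = 0.2011. The half-width is 0.0989. At n = 26 the half-width is 0.1004, so 27 is the smallest n that meets 0.100. The stated 0.201 reproduces.

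**Step 2: attainable counts.** 0.30 × 27 = 8.1, so the neighbours are 8 and 9.

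- 8/27 = 0.2963: L = (0.2963 + 0.03041 − 1.28155 × 0.09102)/1.06083 = 0.1980, half-width 0.0983. This is below 0.20.
- 9/27 = 0.3333: L = (0.3333 + 0.03041 − 1.28155 × 0.09377)/1.06083 = 0.2296, half-width 0.1037. This is above 0.20.

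The split does not depend on the interval method:

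| Lower limit | 8/27 | 9/27 |
|---|---|---|
| Wilson, 1-sided 90% (planned) | 0.198 | 0.230 |
| Wilson, continuity-corrected | 0.183 | 0.214 |
| Wald | 0.184 | 0.217 |
| Clopper-Pearson | 0.181 | 0.212 |
| Wilson with the 95% z value | 0.176 | 0.205 |

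**Step 3: exact binomial probabilities at n = 27.**

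| Requirement | True rate 20% | True rate 30% |
|---|---|---|
| 8 or more | 0.156 | 0.589 |
| 9 or more | 0.074 | 0.423 |

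At a true 30%, P(X = 8) = 0.589 − 0.423 = 0.166. Eight is the mode, since (27 + 1) × 0.30 = 8.4 and its integer part is 8.

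**Step 4: other denominators.** 27/0.85 = 31.8, hence 32 enrolled. The smallest count with a Wilson limit above 0.20, and its exact properties, are:

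| n | Minimum count | Limit | Probability at 20% | Probability at 30% |
|---|---|---|---|---|
| 24 | 8 | 0.224 | 0.089 | 0.44 |
| 25 | 8 | 0.215 | 0.109 | 0.49 |
| 26 | 8 | 0.206 | 0.131 | 0.54 |
| 27 | 9 | 0.230 | 0.074 | 0.42 |
| 28 | 9 | 0.221 | 0.090 | 0.47 |
| 29 | 9 | 0.213 | 0.108 | 0.52 |
| 30 | 9 | 0.205 | 0.129 | 0.57 |
| 31 | 10 | 0.226 | 0.075 | 0.46 |
| 32 | 10 | 0.219 | 0.090 | 0.50 |

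Between 27 and 32, exactly 30% can be observed only at n = 30 (9/30), where it does exclude 20%.

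**The case against.** The strongest reply is that this is a precision calculation at a planning proportion. Such calculations treat p as continuous, the stated limit reproduces, and 27 does follow from the half-width criterion. All of that stands: there is no computational slip.

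The miss is also small. The score statistic for 8/27 against 0.20 is 0.0963/√(0.16/27) = 1.251, which corresponds to about 89.5% one-sided confidence instead of 90%. The plan speaks of preliminary evidence, has no go/no-go rule, and will report 0.198 if 8/27 is seen. It states neither 0.59 nor 0.42; the contrast arises only for a reader who takes 8/27 as sufficient. These points limit the consequence. They do not rescue the sentence, because Section 11.3.2 goes beyond precision to an inference about exceeding 20%, and that inference fails at the nearest observable count.

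Two further points have merit. The failure is specific to the denominator: 8/26 and 9/30 both exclude 20%, which is a reason to tabulate counts, including some below 27. And the 27 versus 32 discrepancy is a separate inconsistency that adds no weight to the main point. It is included because it concerns the same number.

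**Conclusion.** The concern holds. Section 11.3.2 is wrong as written: with 27 analysed patients, the result it describes cannot occur, and the one count that rounds to 30% gives a limit of 0.198, which is 0.002 short of the reference. The effective bar is 9/27 (33.3%), with a half-width slightly above the stated 0.100. If the hypothesised 30% is true, the study reaches that bar with probability 0.42, so it is more likely than not to fall short of the evidence it seeks.

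This rests on exactly 27 EEC patients, independent binary responses and the planned Wilson limit without continuity correction. The reported analysis is not corrupted. The defect is in the justification for N, and it should be corrected before results are read against it. The Section 3 total also conflicts with Sections 11.3.4 and 11.5.2.

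**What to change.** In Section 11.3.2, replace the 30% / 0.201 illustration with text such as:

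> At 27 EEC patients, at least 9 responders (33.3%, lower limit 0.230, half-width 0.104) are needed to exclude 20%; 8/27 (29.6%) gives 0.198 and does not. The probability of 9 or more is 0.42 at a true rate of 30% and 0.074 at a true rate of 20%.

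Keep the Wilson interval. Add the minimum responder counts for n = 27 to 32 (9, 9, 9, 9, 10, 10) with the exact probabilities at 20% and 30% from the table above. Rows for 24 to 26 would be a useful extension in case attrition exceeds 15%. Note that Wilson coverage is approximate and that the exact error at 20% exceeds 10% at n = 29 and 30 (and at 25 and 26, if those rows are shown). Present the table as a description of what the interval can show; it need not become a decision rule.

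In Section 3, state that up to 32 patients will be enrolled to obtain 27 EEC patients.

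The cost is protocol wording only. Endpoint, analysis method and planned enrolment are unchanged, and the stated design figure becomes less favourable.
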